7.5. Specimen Collection

Each study site will adhere to the standards of good clinical laboratory practice, the HPTN-MTN Network Laboratory Manual (available at www.mtnstopshiv.org), DAIDS Laboratory Requirements (available at <http://www3.niaid.nih.gov/research/resources/DAIDSClinRsrch/Labs/>), the MTN-015 Study-Specific Procedures Manual (available at www.mtnstopshiv.org), and site standard operating procedures for proper collection, processing, labeling, transport, and storage of specimens at the local laboratory. Specimen collection, testing, and storage at the site laboratories will be documented when applicable using the Laboratory Data Management System (LDMS).

7.5.1. Local Laboratory Specimens

The specimens listed below will be collected for testing at the local laboratory. Duplicate local laboratory testing for co-enrolled protocols is not required. The results of local laboratory tests that are required for another MTN trial, and that are performed within the allowable visit window for such measures according to this protocol, may be used for MTN-015.

Urine Samples

The Local Laboratory or site research staff will test urine for pregnancy. Sites that have a validated SDA method will test urine for Chlamydia and gonorrhea.

Blood Samples

Study site staff will collect blood samples for the following testing at the local laboratory: CD4+ T-cell counts, plasma HIV-1 RNA, complete blood count, liver and renal function tests, and syphilis serology.

Pelvic Samples

Vaginal pH testing and wet mount testing for bacterial vaginosis, candidiasis and trichomoniasis will be conducted at the sites by clinical and/or laboratory staff who have established proficiency in these procedures per MTN policies and procedures.

Pap smears will be performed at sites with the capacity and expertise to prepare and interpret the smears and provide referrals to appropriate follow-up care to participants with abnormal results.

7.5.2. Regional Laboratory Specimens

Serum or plasma will be stored locally at the site labs for HSV-2 testing. These specimens will be shipped in batches to MTN certified regional labs with the appropriate capacity or the MTN Network Laboratory (NL). Sites that are not certified to perform plasma HIV-1 RNA levels may batch and ship these samples to a certified regional lab or the MTN NL.

7.5.3. Network Laboratory Specimens

Study sites will collect, process, and store the following specimens for later shipment to the MTN Network Laboratory: vaginal swabs, cervicovaginal lavage fluid, serum, plasma, urine and PBMC.

Network laboratory (storage) specimens must be collected for MTN-015 as required. Except for HIV-1 seroconversion plasma from the parent trial, sites

may not use specimens collected or stored for another trial as stored specimens for MTN-015.

Vaginal Swabs

Testing on vaginal swabs will include vaginal flora proteomics and markers of inflammation.

Cervicovaginal Lavage

Testing on cervicovaginal lavage samples will include HIV-1 viral load, determining infectious HIV-1 shedding, standard HIV-1 genotypic resistance testing, and molecular analysis of vaginal flora.

Serum

Testing on serum samples will include HIV-1 ELISA and Western blot (if not previously confirmed in a Network Laboratory).

Plasma

Testing on plasma will include standard genotypic resistance testing, allele-specific polymerase chain reaction (PCR) for relevant drug resistance codons, single genome sequencing, and Herpes Simplex Virus – Type II (HSV-2) type-specific antibody.

Urine

Domestic sites that do not have a validated SDA test will ship urine to the MTN NL for Chlamydia and gonorrhea testing

PBMC

Testing on PBMC will include markers of cell-mediated immunity.

7.6. Specimen Handling

Specimens will be handled in accordance with Requirements for DAIDS Sponsored and/or Funded Laboratories in Clinical Trials <http://www3.niaid.nih.gov/research/resources/DAIDSClinRsrch/Labs/>.

7.7. Biohazard Containment

As the transmission of HIV-1 and other blood-borne pathogens can occur through contact with contaminated needles, blood, and blood products, appropriate blood and secretion precautions will be employed by all personnel in the drawing of blood and shipping and handling of all specimens for this study as recommended by the CDC and NIH. All biological specimens will be transported using packaging mandated by CFR 42 Part 72. All dangerous goods materials, including diagnostic specimens and infectious substances, must be transported according to instructions detailed in the International Air Transport Association (IATA) Dangerous Goods Regulations. This applies to both U.S. and

international sites. Biohazardous waste will be contained according to institutional, transportation/carrier, and all other applicable regulations.

8. ASSESSMENT OF SAFETY

MTN-015 is an observational study involving no investigational products or procedures associated with significant risk to participants. Therefore, few safety concerns are expected as a result of study participation. The study site Investigator of Record is responsible for continuous close safety monitoring of all study participants and for alerting the protocol team if unexpected concerns arise. Study sites will have written procedures for ensuring prompt reporting to the IRB/EC(s), of any unanticipated problem involving risks to subjects or others. No safety events will be captured in the study database.

The Manual for Expedited Reporting of Adverse Events to DAIDS will not be used for this study for the following reasons: 1) this study is observational in nature; 2) this study does not involve a study drug or intervention; and 3) adverse events are not primary or secondary objectives of the study.

The study team will monitor for and track unanticipated problems definitely, probably, or possibly related to study procedures and/or to participation in the study, until participants' time of termination from the study. Study staff will provide clinically appropriate treatment and/or referrals should any such problems occur.

For MTN-015 participants both enrolled and not enrolled in a parent study, any unanticipated problems will be reported to the DAIDS Medical Officer at the same time as the problems are reported to the responsible site IRB/Ethics Committees (ECs) overseeing the research according to pre-established procedures as required by 45 CFR 46. Participants co-enrolled in MTN-015 and a parent study will have serious adverse events (SAEs) and Expedited Adverse Events (EAEs) considered reportable in the parent study reported via the safety reporting system utilized by the parent study. Once a participant is no longer enrolled in the parent study, any unanticipated study-related injury will be reported to the site IRB/EC and DAIDS Medical Officer.

As this study will enroll only HIV-infected participants, participants may experience social harms — non-medical adverse consequences — as a result of their participation in the study. Information on social harms will be collected and captured in the study database. Social harms that are judged by the Investigator of Record to be serious or unexpected will be reported to responsible site IRB/ECs at least annually, or according to their individual requirements. In the event that a participant reports social harm, every effort will be made by study staff to provide appropriate care and counseling to the participant, and/or referral

to appropriate resources for the safety of the participant as needed. The SDMC (SCHARP) will provide listings of social harms reported by study participants to the protocol team at a minimum of every 6 months per any applicable DAIDS requirements.

Relationship to study participation or procedures will be assessed based on the following definitions:

- **Possibly related:** unanticipated problem and study participation/procedures are reasonably related in time, and the unanticipated problem could be explained equally well by causes other than study participation/procedures.
- **Probably related:** unanticipated problem and study participation/procedures are reasonably related in time, and the unanticipated problem is more likely explained by study participation/procedures than by other causes.
- **Definitely related:** unanticipated problem and study participation/procedures are related in time, and a direct association can be demonstrated with study participation/procedures.

9. CLINICAL MANAGEMENT

9.1. HIV-1 Infection

Study participants will be referred for HIV-1 care and treatment according to local guidelines at the time of HIV-1 diagnosis in the parent microbicide trial. Written site-specific operating procedures for referral for HIV-1 care and treatment are in place at each study site. Study site investigators have identified facilities offering psychological and social services and medical care, including antiretroviral therapy, to people infected with HIV-1 in the study countries. Some of the research sites are part of health care institutions that provide HIV-1 care and support, and can refer women to those services. Other sites have established referral agreements with programs to expand access to antiretroviral therapy, such as those funded by the US President's Emergency Plan for AIDS Relief (PEPFAR). The level of care provided at the referral sites will be at a level that meets or exceeds the community standard for HIV-1 care. At every study visit, study staff will actively follow-up on prior referrals to HIV-1 care and support services, to determine whether the participant sought the care to which she was referred, determine the outcome of the referral, and determine whether additional referrals are needed. Additional counseling also may be needed to help ensure the participant receives appropriate care. All follow-up actions, outcomes, counseling, and plans for next steps should be documented in detailed chart

notes. Results of laboratory testing in MTN-015 may be helpful in clinical management; these results will be provided to the participant and her medical provider in real-time.

9.2. Reproductive Tract Infection

Participants who are diagnosed with a sexually transmitted infection (STI) or other reproductive tract infection (RTI) will be provided treatment in accordance with current World Health Organization (WHO) guidelines, free of charge. Observed single-dose treatment will be provided whenever possible. Participants with STIs will be encouraged to refer their partners for testing and treatment if applicable. Sites will not be required to offer or provide treatment for asymptomatic bacterial vaginosis or candida noted at study visits.

9.3. Pregnancy

Participants who are found to be pregnant during the study period will continue to be followed. Study sites will refer pregnant participants to providers of obstetric and gynecologic care for counseling and further related care. Every effort will be made to facilitate access to PMTCT. Any PMTCT medication received by the participant will be documented as a concomitant medication. Protocol-defined gynecologic exams and pelvic specimen collection will not be performed on pregnant participants if the following symptoms are reported: vaginal bleeding or spotting, suspected or documented rupture of membranes, or active labor; these participants will be referred to an obstetric/gynecologic care provider.

9.4. Provision of Test Results

Because laboratory testing will be performed at all scheduled study visits, a post-visit contact is required after each visit to provide participants with their test results, clinically relevant post-test counseling, and/or clinically indicated treatment. Study staff may complete these contacts at the study site or at community-based locations, depending on site capacities and site and participant preferences. All contacts will be documented in participant study records and written documentation of test results will be provided upon request to participants and/or their primary HIV-1 care providers.

9.5. Criteria for Discontinuation of Study Participation

Participants may voluntarily withdraw from the study for any reason at any time. The site investigators may withdraw participants from the study to protect their safety, and/or if participants are unable or unwilling to comply with required study procedures. The investigators may withdraw a participant from the study if any condition in the opinion of the investigator would impose a health risk to the participant. Participants also may be withdrawn if the study sponsors, government or regulatory authorities (including the Office of Human Research

Protection (OHRP)), or site IRBs/ECs terminate the study prior to its planned end date. Site investigators are required to consult the Protocol Chair and Protocol Biostatistician prior to the termination of any study participant. Study staff will record the reason(s) for all withdrawals in participants' study records. In the event that participants who voluntarily withdraw from the study wish to re-join the study, they may resume study procedures and follow-up.

The criteria for discontinuation of further study procedures for an individual participant are:

- Request by participant to withdraw
- Clinical reasons determined by the physician
- Lost to follow-up
- Participant repeatedly non-compliant with study procedures as prescribed

Participants will be asked to complete a final study visit.

10. STATISTICAL CONSIDERATIONS

10.1. Overview and General Design

This is a prospective cohort study of seroconverters identified in microbicide trials. Currently, participants will come from two trials: HPTN 035 and HPTN 059.

The targeted number of seroconverters (i.e. HIV endpoints) in HPTN 035 is 192 while the expected number of HIV endpoints in HPTN 059 is much smaller (0 to 2 seroconverters only). Given that it is difficult to anticipate the number of seroconverters generated by future MTN trials, we will conservatively estimate the available sample size at 192.

10.2. Study Endpoints

10.2.1. Primary Endpoint

Virologic Response

Consistent with the primary study objective, plasma HIV-1 RNA 12 months after identification of HIV-1 seroconversion will be the primary endpoint. Comparison of the plasma HIV-1 RNA level 12 months after HIV-1 seroconversion between active microbicide and placebo/control groups is the primary objective of this study.

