4. STUDY DESIGN

4.1. Identification of Study Design

MTN-015 is a multi-site, prospective observational cohort study. Potential participants will be offered enrollment in MTN-015 following identification of HIV-1 seroconversion in the parent trial (the trial from which they were identified). For the purposes of this protocol, date of seroconversion is defined as the date of HIV-1 seroconversion used in the parent trial. The participant's HIV-1 seroconversion should be confirmed according to the HIV-1 testing algorithm of the parent trial. Study participants may be followed concurrently in the MTN parent trial and MTN-015 for the duration of the parent trial and subsequently continue in MTN-015 for the duration of MTN funding. Participants in MTN-015 may participate in other clinical trials including HIV-1 treatment trials.

This study will utilize two follow-up visit schedules: one based on the date of identification of seroconversion in the parent study and one based on initiation of ART use; see Section 7 for details on each schedule. Participants who have not initiated use of ART at the time of enrollment in MTN-015 will follow the schedule based on the date of identification of seroconversion. Participants who have initiated use of ART at the time of enrollment in MTN-015 will follow the schedule based on the date of ART initiation. Participants who initiate use of ART during follow-up in MTN-015 will have their follow-up schedule adjusted to the schedule based on initiation of ART use. Study sites will be provided with computerized tools (either spreadsheet or web-based) to assist them in determining the appropriate visit schedule to follow for each participant. Past or current use of most ART regimens will constitute initiation of ART for purposes of this study; however, use of single dose nevirapine for PMTCT will not constitute initiation of ART for purposes of this study.

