7.2. Follow-up Visits

This study utilizes two follow-up visit schedules, one based on the date of identification of seroconversion in the parent study and one based on initiation of ART use.

- Participants who have not initiated use of ART at the time of enrollment in MTN-015 will follow the schedule based on the date of identification of seroconversion, which is described in Section 7.2.1. On this schedule, follow-up visits occur at Months 1, 3, and 6 after the date of identification of seroconversion, and every 6 months thereafter. Participants may enroll anytime after seroconversion. Following the enrollment visit, the subsequent visits will be scheduled according to the seroconversion date (for example, a participant who enrolls 4 months after seroconversion would have a second visit at 6 months after seroconversion (2 months after enrollment) and then every 6 months).
- Participants who have initiated use of ART at the time of enrollment in MTN-015 will follow the schedule based on the date of ART initiation, which is described in Section 7.2.2. On this schedule, follow-up visits occur at Week 2 and Months 1, 3, and 6 after the date of ART initiation, and every 6 months thereafter.
- Participants who initiate use of ART during follow-up in MTN-015 will follow the schedule in section 7.2.1, and then switch to the schedule in Section 7.2.2 after initiation of ART use.

As it will not always be possible to conduct follow-up visits on the target dates specified above, visits may be completed at any time during allowable visit windows. For both the non-ART and ART visit schedules, the allowable visit windows are contiguous and extend from the midpoint of one visit interval to the midpoint of the next visit interval. For example, the Month 24 visit window extends from Month 21 through Month 27. For participants who do not complete scheduled visits within the allowable window, the visit will be considered missed and relevant case report forms will be completed to document the missed visit. Missed visits will not be considered protocol violations.

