10.6.2. Data Analysis

Primary Analyses

Descriptive analyses of the seroconverters will include calculation of the mean and median viral load by active microbicide and placebo/control groups. A simple t-test can be used to compare log-transformed viral load levels between these two groups. However, caution must be exercised in the interpretation of any difference (or lack of difference) found. Although the overall active microbicide and placebo/control groups should be comparable at baseline (in the parent study) due to randomization, individuals who seroconvert in the active microbicide group may not be comparable to individuals who seroconvert in the placebo/control group. Approaches described by Gilbert et al, *Biometrics*, 2003 will be used for isolating the effect of an intervention on post-seroconversion outcomes.^{xvi} Furthermore, the primary analysis will be restricted to

seroconverters that have not initiated ART in the first 12 months after seroconversion.

Linear regression using the log-transformed viral load levels as the outcome and baseline or other covariates (e.g. CD4+ T-cell) will be used to compute adjusted differences between the active microbicide and placebo/control groups. The interpretation of these adjusted differences is subject to the same cautions noted above.

Sub-group exploratory analyses will be performed to explore difference between type of products and type of controls. Mainly, seroconverters will be grouped by the type of intervention received: (1) PRO2000, (2) BufferGel, (3) Placebo gel, and (4) Condom only.

Secondary Analyses

Secondary analyses of CD4+ T-cell counts will be virtually identical to those described for viral load levels above, although it is typically not necessary to log-transform CD4+ T-cell levels to obtain valid inferences. Descriptive statistics will be used to characterize overall CD4+ T-cell levels and levels within subgroups. T-tests and linear regression will be used to obtain unadjusted and adjusted estimates of the treatment effect. Again, the interpretation of these differences is subject to the same cautions noted above for the primary analyses.

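### The ART exclusion in the primary analysis is a fixed 12-month cut, not tied to ART status when the analysed RNA sample is drawn

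*Protocol*

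**What the plan says.** Four parts of the protocol bear on which viral load enters the primary comparison.

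- **Endpoint (10.2.1).** One sentence says "plasma HIV-1 RNA 12 months after identification of HIV-1 seroconversion will be the primary endpoint". The next counts from seroconversion: "Comparison of the plasma HIV-1 RNA level 12 months after HIV-1 seroconversion between active microbicide and placebo/control groups is the primary objective".
- **Origin date (4.1).** The "date of seroconversion is defined as the date of HIV-1 seroconversion used in the parent trial". The protocol does not say whether this equals the date of identification.
- **Visits (7.2).** There are two schedules, "one based on the date of identification of seroconversion in the parent study and one based on initiation of ART use". The same bullet that describes the pre-ART schedule later says that "the subsequent visits will be scheduled according to the seroconversion date". Women who begin ART during follow-up "then switch to the schedule in Section 7.2.2 after initiation of ART use". On timing, "the allowable visit windows are contiguous and extend from the midpoint of one visit interval to the midpoint of the next visit interval"; the worked example gives Months 21 to 27 for Month 24.
- **ART restriction (10.3 and 10.6.2).** The primary analysis is limited to "seroconverters that have not initiated ART in the first 12 months after seroconversion". Section 10.3 expects under 10% of women to start ART in that period and puts power at 76% or more after a 10% exclusion.

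The primary objective (3.1) concerns ART-naive participants.

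**The concern.** What makes a viral load ART-naive is whether ART had begun when the blood was drawn. The protocol instead tests whether ART began before a fixed calendar point, while the sample itself may fall up to three months either side of that point. The two tests can disagree in both directions.

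The exclusion of valid values matters more in principle. It conditions on an event after the outcome. Section 9.1 returns laboratory results to the participant and her provider in real time, and Section 13.3 says that CD4+ and RNA monitoring may open the way to earlier treatment. A Month 10 result can thus contribute to the ART start that removes that same result from the analysis. This adds to the post-randomisation selection that Section 10.6.2 already warns about.

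An on-ART value admitted as ART-naive would be unusually low. It would add variance, and it would shift the difference in either direction if such values were unbalanced between groups.

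**Working it through.** **The protocol's own figures.** Inputs from 10.3: variance components 0.52 and 0.096, so 0.616 for one observation per person; groups of 46 and 92; difference 0.4; two-sided alpha 0.05.

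- Sample size: (192 − 20) × 0.85 × 0.95 = 138.9, stated as 138.
- Standard error: √[0.616 × (1/46 + 1/92)] = 0.1417, so 0.4/0.1417 = 2.82. Noncentral t power is 80.0% (stated 80%).
- After a 10% ART exclusion, 41.4 and 82.8 women: power 75.7% by noncentral t and 76.3% by the normal approximation (stated 76%).

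**The window.** The visits next to Month 12 are Months 6 and 18. The midpoints are Months 9 and 15.

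**The rule applied to two women.**

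| RNA drawn | ART starts | In Month 12 window? | ART-naive at sample? | Passes the 12-month cut? |
|---|---|---|---|---|
| Month 10 | Month 11 | yes | yes | no: valid value dropped |
| Month 13 | Month 12.5 | yes | no | yes: not expressly barred |

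Both rows hold even if the identification and seroconversion dates coincide.

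**How many women.** Assume a constant rate of starting ART that reaches the 10% ceiling at Month 12: monthly hazard −ln(0.9)/12 = 0.00878.

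- Starts in Months 9 to 12: 138 × (0.9240 − 0.9000) = 3.3.
- Starts in Months 12 to 15: 138 × (0.9000 − 0.8766) = 3.2, or 2.6% of those ART-naive at Month 12.
- If instead all 10% start evenly over Months 6 to 12: 138 × 0.10 × 3/6 = 6.9 in Months 9 to 12.

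**Cost of discarding.** Adding 3.3 or 6.9 women to 124.2, in the ratio 1:2, raises power from 76% to 77% or 78%. This is a ceiling, because only women sampled before they started ART can be recovered.

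**Cost of admitting.** Let p be the share of values on ART and D the fall in log10 RNA. Neither is in the protocol. If visits are uniform over Months 9 to 15 and starts uniform over 12 to 15, then 0.5 × 0.5 = 25% of those starters are sampled after starting, so p = 0.25 × 2.6% = 0.65%. If visits cluster at Month 12 (triangular), the share is 0.5 × 1/3 = 17% and p is about 0.4%. I take p from 0.4% to 1% and D from 1 to 2. Variance becomes 0.616 + p(1 − p)D² and the difference 0.4(1 − p).

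| p | D | Variance | Power at 46/92 |
|---|---|---|---|
| none | – | 0.616 | 80.0% |
| 0.4% | 1 | 0.620 | 79.5% |
| 0.4% | 2 | 0.632 | 78.7% |
| 1% | 1 | 0.626 | 78.6% |
| 1% | 2 | 0.656 | 76.7% |

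The loss is 0.6 to 3.3 points. Starting from the ART-excluded groups of 41.4 and 82.8 it is 0.6 to 3.5 points.

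**The case against.** **On-ART values are already ruled out.** The objective is confined to ART-naive women, and Sections 7.2 and 7.2.1 move a woman to the ART schedule once she starts, so her next visit is not a Month 12 post-seroconversion visit. This largely stands. A reader might infer that the plan will analyse on-ART values, but the documents do not support that. They only lack an operative rule against it.

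**The exclusion is deliberate and its price is stated.** True: Section 10.3 gives the 76%. That figure prices the lost numbers. It does not address dropping a measured outcome because of a later event.

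**The dates may be the same.** Section 7.2 uses both terms for one schedule, as if they were synonyms. A reader might infer from the three-monthly testing (2.2.2) and the stored enrolment specimens (4.1) that the dates differ by months. The protocol does not show this, since the parent trials' dating rules are not in it. If the dates coincide, only loose wording remains.

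**Sample selection belongs in the SAP.** Which sample represents Month 12 can indeed be settled there. The 12-month exclusion, however, is fixed in the protocol, and an SAP that follows it inherits the mismatch.

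**The replacement has its own flaw.** A woman who starts ART within the window would be kept or dropped according to when she happened to attend. This is a real but small drawback.

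**Conclusion.** The point holds as a defect of definition with a small effect. As written, the rule does discard valid ART-naive Month 12 values. That on-ART values could enter is only a possibility. The inconsistent origin matters only if the parent trial's seroconversion date differs from the identification date.

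About 3 of 138 women, and at most about 7, start ART in Months 9 to 12, and about 3 in Months 12 to 15. Recovering samples is worth about 1 to 2 points of power, and admitted on-ART values would cost roughly 1 to 3. These figures rest on the 10% ceiling, the assumed timing of ART starts and visits, and the assumed fall on ART. A much larger power loss might be inferred by letting nearly every woman who starts in Months 12 to 15 contribute an on-ART value. That is implausible when the visit target is Month 12 and most would already have been sampled. Table 7 and the 76% figure are correct for their inputs.

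**What to change.** 1. Name one origin date, of the sponsor's choosing, and use it for the endpoint (10.2.1), the visit windows (7.2) and the ART restriction (10.3 and 10.6.2).
2. Replace the calendar exclusion in 10.3 and 10.6.2 with: *the primary analysis uses the RNA sample closest to 12 months within the Month 12 window that was drawn on or before the date of ART initiation.*
3. Keep the fixed 12-month exclusion as a sensitivity analysis, which also shows whether the dependence on visit timing matters.

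The cost is wording only. RNA is drawn at every scheduled visit and an antiretroviral treatment record is already part of the schedule (Appendix I). No visit, test or sample size changes.
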